Lead Site: N/A

Performance Site: N/A

SECTION B: RESEARCH METHODOLOGY

B1. ABSTRACT

[figure not shown]
Two recent investigations from our laboratory have consistently observed a reduction (30-50%) in the rate of exogenous glucose oxidation in native lowlanders performing metabolically-matched, steady-state exercise at high altitude (HA) compared to sea level (SL). Accompanying lower rates of exogenous glucose oxidation at HA were increases in circulating glucose and insulin concentrations, and reduced glucose rate of disappearance and metabolic clearance rate. Apparent hypoxia-induced insulin insensitivity along with alterations in glucose kinetics suggests reduction in glucose uptake by the peripheral tissue is a primary factor contributing to reductions in exogenous glucose oxidation at HA. As such, the primary objective of this study is to determine the ability of an insulin sensitizer (Pioglitazone, PIO) to enhance exogenous glucose oxidation and metabolic clearance rate during metabolically-matched, steady-state exercise during acute HA exposure compared to placebo (PLA) in native lowlanders. Secondary objective of this study will be to assess the impact of PIO on markers of inflammation and iron status compared to PLA. This randomized crossover placebo control double blinded study will examine substrate oxidation and glucose kinetic responses to ingesting supplemental carbohydrate (glucose) during metabolically-matched, steady-state exercise with acute (~5 h)

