Steady-State Treadmill Exercise: Results from a $\dot{\text{V}}\text{O}_{\text{peak}}$ assessment under HA conditions will be used to prescribe intensities for treadmill exercise on experimental trial days utilizing ACSM equations to estimate the speed and grade of the treadmill. Volunteers will complete 80-min of metabolically-matched, steady-state exercise at 55 \pm 5% of their $\dot{\text{V}}\text{O}_{\text{peak}}$ determined at HA. A practice session will be conducted during the baseline period to confirm prescribed speed and grade are appropriate to induce target $\dot{\text{V}}\text{O}_2$ and allow the research team to make modifications to prescribed speed and grade if needed to induce target $\dot{\text{V}}\text{O}_2$. The practice session will range ~40-80 minutes in length. The speed and grade determined during the practice session will be used to induce the same absolute intensity between study arms. The mode, duration, and intensity of steady-state exercise were chosen to mimic our past investigations (3, 4).

Carbohydrate Tracer Studies: After a 10 hr overnight fast, two catheters will be placed into the lower arm (one in each arm). One arm will be used for infusion of 6,6-[$^2\text{H}_2$] glucose tracer and the other will be used for blood sampling. Following an initial blood and breath sample collection to determine background enrichments, a primed, continuous infusion of 6,6-[$^2\text{H}_2$] glucose (Cambridge Isotope Laboratory, Andover, MA, USA) will begin (prime, 82.2 $\mu\text{mol}\cdot\text{kg}^{-1}$; continuous rate, 0.78 $\mu\text{mol}\cdot\text{kg}^{-1}\cdot\text{min}^{-1}$) (24, 25) for 2 hrs before and during exercise. Volunteers will complete 80-min of steady-state exercise on a treadmill, with $\dot{\text{V}}\text{O}_2$, $\dot{\text{V}}\text{CO}_2$, HR, and SaO_2 measured at approximately 5, 20, 40, 50, 60, and 75 min. During exercise volunteers will consume a glucose beverage at 1.8 g/min. Drinks will contain 145 g glucose, with a total volume of 1450 mL. The drink will be consumed in four boluses throughout the 80-min of steady-state exercise (0, 20, 40, and 60 min). The first bolus will be 550 mL, with the remaining three being 300 mL. The glucose beverage consumed during exercise will be enriched with 200 mg ^{13}C -glucose (Cambridge Isotope Laboratory) to increase the isotopic enrichment well above natural levels and optimize the measurement of exogenous glucose oxidation.

Figure 3: Carbohydrate Tracer Studies

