Blood Sampling (credentialed procedure): Blood samples will be collected using an indwelling catheter kept patent using IV saline at approximately at approximately -300, -120, -30, 0, 20, 40, 60, 80, and 140 min during exercise by a USARIEM credentialed phlebotomist. Baseline blood sampling will occur after a 10-hr overnight fast on experimental trial days. A total of 18 blood samples will be completed during this study taking ~340 mL of blood sampled from each volunteer over the experimental trial days (**Table 3**). Blood samples will be used for isotope analysis assessment, substrate and hormone responses, and iron markers (**Table 3**).

For glucose kinetic analysis, the tracer/tracee ratio (6,6-[²H]₂] glucose/glucose) using gas-chromatography-mass spectrometry (GCMS; Metabolic Solutions, Inc., Nashua, NH) (24), while ¹³C/¹²C in plasma glucose will be measured using isotope-ratio mass spectroscopy (IRMS; Metabolic Solutions).

Breath Sampling (non-credentialed procedure): Breath samples will be collected at approximately -300, 0, 20, 40, 45, 50, 55, 60, 65, 70, 75, and 80 min during exercise to determine exogenous glucose oxidation using single-patient breath collection bags (Quin-Tron Instrument Company, Milwaukee, WI, USA). Baseline breath sample will also be collected prior to correct for background of naturally occurring ¹³C. The natural enrichment of the glucose ingested and the ¹³C/¹²C in expired gas samples will be analyzed using isotope-ratio mass spectroscopy (Metabolic Solutions, Inc., Nashua, NH).

B5.4 Data Collection

Table 2. Outcome Variables

Data Element/Variable	Source	Operational Specification
Anthropometric data	Direct measurement	Height, weight, body composition
Substrate oxidation	Blood and breath	Glucose turnover, carbohydrate, fat, and protein oxidation
Metabolic response	Blood	Substrate analytes, hormones, inflammation, iron status

Table 3. Blood Analytes

Analyte	Time points (min)								
	-300	-120	-30	0	20	40	60	80	140 ⁴
Glucose ¹	x	x	x	x	x	x	x	x	x
Insulin ²	x			x	x	x	x	x	x
Free fatty acids ²	x			x	x	x	x	x	x
Lactate ²	x			x	x	x	x	x	x
Glycerol ²	x			x	x	x	x	x	x
Norepinephrine ²	x			x	x	x	x	x	x
Epinephrine ²	x			x	x	x	x	x	x
Hemoglobin ¹	x			x				x	
Hematocrit ¹	x			x				x	
¹³ C-glucose ³				x	x	x	x	x	x
6,6-[² H ₂] glucose ³		x	x	x	x	x	x	x	x
PBMC ¹	x			x				x	x
TNF α ¹	x			x				x	x
IL-6 ¹	x			x				x	x
IL-10 ¹	x			x				x	x
Hemooxygenase 1 ¹	x			x				x	x
Adiponectin ¹	x			x				x	x
Erythropoietin ¹	x			x					

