$$\text{Endogenous glucose } R_a = \text{Total } R_a - \text{Exo } R_a$$

$$\text{Metabolic Clearance Rate (MCR)} = \text{Glucose } R_d / ((C_2 + C_1) / 2)$$

Where F represents the infusion rate of 6,6-[²H₂] glucose; pV is the effective volume of distribution for glucose, C₁ and C₂ are plasma glucose concentrations at t₁ and t₂, respectively, E₁ and E₂ are plasma enrichments of 6,6-[²H₂] glucose at t₁ and t₂, respectively, and E_d and E_p are tracer enrichments of U-¹³C-glucose from the test drink and plasma, respectively.

Calculations of Carbohydrate and Fat Oxidation

Carbohydrate and fat oxidation rates will be calculated from $\dot{V}O_2$ (L/min) and $\dot{V}CO_2$ (L/min) during the 80-min exercise bout as described by Jeukendrup and Wallis (27):

$$\text{Fat oxidation (g/min)} = (1.695 \times \dot{V}O_2) - (1.701 \times \dot{V}CO_2)$$

$$\text{Carbohydrate oxidation (g glucose/min)} = (4.585 \times \dot{V}CO_2) - (3.226 \times \dot{V}O_2)$$

Calculations of Exogenous and Endogenous Glucose Oxidation

Exogenous and plasma glucose oxidation will be calculated as (7):

$$\text{Exogenous glucose (g/min)} = \dot{V}CO_2 [(R_{exp} - R_{ref}) / (R_{exo} - R_{ref})] / k$$

$$\text{Plasma glucose (g/min)} = \dot{V}CO_2 [(R_{exp} - R_{ref}) / (R_{glu} - R_{ref})] / k$$

where $\dot{V}CO_2$ is in L/min, R_{exp} is the observed isotopic composition of expired CO₂, R_{ref} is the isotopic composition of expired CO₂ at rest before ingestion of the first dose of ¹³C-glucose, R_{exo} is the isotopic composition of the exogenous glucose ingested, R_{glu} is the isotopic composition of plasma glucose, and k (0.747 L/g) is the volume of CO₂ provided by the complete oxidation of glucose. Total endogenous glucose oxidation can be calculated by subtracting exogenous glucose oxidation from total CHO oxidation.

Endogenous glucose oxidation derived from muscle and liver can be determined by subtracting plasma glucose oxidation from total carbohydrate oxidation (muscle), and subtracting exogenous carbohydrate oxidation (liver) from plasma glucose oxidation (7). The first 40 min of steady-state exercise will allow for equilibration between the ¹³C/¹²C in expired CO₂ and the ¹³C/¹²C in CO₂ produced in tissues (28). Thus, endogenous glucose oxidation will only be calculated from samples obtained in the last 40 min of steady-state exercise (40 to 80 min).

Blood Analytes

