5.7.1.3 Any device not approved by the FDA

N/A

B5.7.2 Drugs

B5.7.2.1 FDA-approved and used in accordance with the approved labeling

B5.7.2.2 FDA-approved and used in a manner not in accordance with its approved labeling
Pioglitazone, Thiazolidinedione, Takeda Pharmaceutical Company

B5.7.2.3 Any drug not approved by the FDA

N/A

B8 Statistical Analysis

B5.8.1 Sample Size Estimation

Based on results of exogenous carbohydrate oxidation and MCR rate between SL and HA in our previous investigation (3, 4), a sample size of 8 is required to achieve 80% power (**Table 4**). We will request to enroll up to 24 individuals to account for withdrawals from the study.

Table 4: Previous study effect sizes

Study	Outcome	Delta	Effect Size	Sample Size
Young et al. (4)	Exogenous Glucose Oxidation	0.35 ± 0.21	1.11	7
Margolis et al. (3)	Exogenous Glucose Oxidation	0.09 ± 0.06	0.95	8
Margolis et al. (3)	MCR	3.1 ± 2.0	0.98	7

B5.8.2 Data analysis

Statistical analyses will be conducted using either SPSS (IBM Corp. Armonk, NY), SAS 9.3 (SAS Institute Inc., Carey, NC), or equivalent. Shapiro Wilks will be used to assess all data for normality. Data that are not normally distributed will be log transformed for statistical analysis. Paired T tests will be used to assess effects of study arms (HA+PIO vs. HA+PLA) on chamber conditions (barometric pressure, temperature, and humidity), oxygen saturation, heart rate, $\dot{V}O_2$, $\dot{V}CO_2$, respiratory exchange ratio, ventilation exchange, total glucose and fat oxidation, plasma glucose, muscle, and liver oxidation. Mixed Model repeated measures ANOVA will be used to assess the effects of condition, time, and their interactions for breath ^{13}C -enrichments, exogenous glucose oxidation, and blood analytes. Bonferroni adjustments for multiple comparisons will be performed if significant interactions are observed.

SECTION C: HUMAN RESEARCH PROTECTIONS

C1. RECRUITMENT AND CONSENT

C1.1 Identification and Selection of Subjects

Volunteers will be recruited from the federally and non-federally employed civilian population, the Natick Human Research Volunteer (HRV) Pool, NSSC active duty military personnel, and the active duty population located at other military organizations, to include, but not limited to coordination with the NSSC Soldier and Squad Optimization and Integration Team (SSO-IT).

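### B5.8.2 lets a Shapiro-Wilk test on unspecified data decide whether an outcome is logged; fix the scale in advance and check normality on differences or residuals (minor)

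*Combined protocol and SAP*

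**What the plan says.** B5.8.2 (Data analysis) has two consecutive sentences on this point: "Shapiro Wilks will be used to assess all data for normality" and "Data that are not normally distributed will be log transformed for statistical analysis". The second is unconditional. The section gives no significance level for the normality test. It does not say what is tested (raw values, paired differences or residuals) or whether arms and times are pooled, and it has no fallback if a log cannot be taken. No other section limits the rule.

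The same section assigns paired t tests to total glucose, fat, plasma glucose, muscle and liver oxidation, among others. For breath enrichment, exogenous glucose oxidation and blood analytes it says "Mixed Model repeated measures ANOVA will be used to assess the effects of condition, time, and their interactions".

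Exogenous glucose oxidation is the first outcome named in hypothesis 1 (B4). It is defined in g/min (B5.4), and Table 4 (B5.8.1) plans on absolute deltas for it and for MCR.

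**The concern.** The test may be applied to the wrong object. A paired t test needs within-volunteer differences that are close to normal, and a mixed model needs this of its residuals. Neither needs raw values to be normal. Repeated raw values from 8 volunteers are clustered. When pooled over arms and times, they can fail Shapiro-Wilk because volunteers differ, because oxidation changes over time or because the drug works, even if every error is normal.

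At stake is the estimand. On the raw scale the trial estimates a difference in g/min; after a log it estimates a ratio of geometric means. Two analysts who both follow B5.8.2 could report the main outcome on different scales.

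**Working it through.** **1. The plan's own figure.** Table 4 lists deltas of 0.35 ± 0.21, 0.09 ± 0.06 and 3.1 ± 2.0, with effect sizes 1.11, 0.95 and 0.98 and sample sizes 7, 8 and 7. With the listed effect sizes, a paired t test for 80% power at alpha 0.05 (assumed; not stated) needs n = 7, 9, 8 one-sided and 9, 11, 11 two-sided. The stated 8 is therefore roughly reproduced one-sided. Table 4 contains absolute differences and no ratios, so the planning scale is a difference.

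**2. Shapiro-Wilk on 8 values** (5% level assumed; 10,000 replicates). It rejects in 5.1% of normal samples, 10.6% of lognormal samples with log-SD 0.3 and 17.7% with log-SD 0.5. It misses most real skewness and still fires about once in 20 when there is none.

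**3. Testing each arm-by-time cell.** If cells were independent, the chance of at least one failure under normality would be 1 − 0.95^k. With 2 arms × 4 times, k = 8 gives 1 − 0.663 = 0.337. With 2 × 9, k = 18 gives 1 − 0.397 = 0.603. Correlation within volunteers lowers both.

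**4. Simulation for exogenous glucose oxidation.** There are 8 volunteers, 2 arms and exactly normal errors, with 1,500 replicates per setting. Inputs:
- Reduction r = 30%, from B1: "consistently observed a reduction (30-50%) in the rate of exogenous glucose oxidation".
- Placebo level at altitude = (delta / r) × (1 − r): 0.09 / 0.30 × 0.70 = 0.21 g/min and 0.35 / 0.30 × 0.70 = 0.82 g/min.
- SD 0.06 or 0.21 (Table 4), read as the SD of the paired difference (assumed).
- Also assumed: between-arm correlation 0.5; residual SD 0.3 of that SD; course flat or rising from 0.85 to 1 of plateau; times 40, 50, 60, 75 min or every 5 min from 40 to 80.
- Standardised drug effect 0 or 1.16. The value 1.16 is chosen because it gives exact two-sided power of 0.803 at n = 8.
- The condition test is a t test on each volunteer's mean difference, standing in for the mixed model.
- Volunteers with any value at or below 2% of the placebo level were redrawn (0-1% of draws).

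| What is tested | Log forced, 4 times | Log forced, 9 times | Power lost, 4 / 9 times |
|---|---|---|---|
| Raw values, pooled | 0.293-0.477 | 0.649-0.837 | 0.014-0.020 / 0.024-0.027 |
| Raw values, any cell | 0.245-0.289 | 0.398-0.435 | 0.008-0.012 / 0.013-0.024 |

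Residuals fail in 0.031-0.051 of trials and mean differences in 0.043-0.061. The significance verdict differs between the rule and a fixed raw scale in 0.015-0.045 of trials. Over all settings run, including a 50% reduction, type I error is 0.034-0.065 with the rule and 0.040-0.065 without it.

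**5. Sensitivity to the assumptions.** Repeat runs of this design gave pooled rates of 28-47% (4 times) and 63-85% (9 times), and cell rates of 26-46%. A run with different SDs and time courses (9-10 times) gave pooled rates from 6% to over 99% and cell rates of 50-55%. Residuals or differences stayed at about 4-6% there. The raw-value rates depend on the inputs; the residual and difference rates hardly do.

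**6. Paired t outcomes.** The setting is 8 pairs with lognormal levels (log-SD 0.3 / 0.5) and normal differences, 4,000 replicates per setting. Testing each arm's raw values forces the log in 0.120-0.152 / 0.203-0.251 of trials, against 0.044-0.054 when differences are tested. Power is 0.792-0.810 on the fixed scale and 0.788-0.803 / 0.774-0.782 under the rule. The verdict changes in 0.009-0.013 / 0.030-0.045.

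**7. When the log does not exist.** From the formulas in B5.4, fat oxidation is zero at VCO2/VO2 = 1.695 / 1.701 = 0.9965 and negative above it. Muscle and liver oxidation are differences of two estimates. Exogenous oxidation is zero or negative when expired enrichment is at or below its reference. B5.8.2 has no rule for these values.

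**The case against.** The best reply is that a Shapiro-Wilk check followed by a log is a common convention, that it is stated in advance here, and that a competent analyst would test differences or residuals. The log would then be triggered in only about 3-6% of trials, and even under the worse readings little changes. The point about size stands. The rest does not remove the concern. The text says all data and makes the log mandatory, and even a check on residuals would switch the scale by chance about once in 20 trials.

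A reader might infer more than the documents support:
- *That the plan tests raw values.* It does not say so. That is the plain reading, but only one of several.
- *That the high pooled rates are bad luck.* They are not chance alone. Clustering, time course and a real drug effect also produce them.
- *That false positives rise.* The simulations show no inflation.
- *That much power is lost because non-positive rates drop out on the log scale.* This would need a deletion rule that the plan does not contain and an additive model that yields negative oxidation rates. No such loss is claimed.
- *That the simulated rates are predictions.* The 40-80 min window, the correlation, the residual SD, the time course and the effect of 1.16 are assumptions. Table 4's listed effect sizes are 0.95-1.11, and the mixed model itself was not simulated.

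**Conclusion.** The point holds as a minor one. Confidence is high on the wording gap and moderate on the figures. B5.8.2 makes an unspecified normality test the only thing that sets the analysis scale, although the planned methods need normality only of differences or residuals. With normal errors and a 30% reduction, testing raw values forces a log in roughly 25-48% of trials (4 times) or 40-84% (9 times), against about 3-6% for residuals or differences. The cost is about 1-3 points of power and a changed verdict in about 2-5% of trials. The main harm is that the estimand for exogenous glucose oxidation is left to a test result. The problem of non-positive values is conditional: it arises only if such values occur and a log is called for.

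**What to change.** Replace the two sentences in B5.8.2 with:

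> Exogenous glucose oxidation, the other oxidation rates and MCR are analysed untransformed, on the scale of Table 4. The scale of every other outcome is named before any outcome data are examined. Normality is inspected on paired differences (paired t tests) or model residuals (mixed model), not raw values, and does not change the scale of the primary analysis. A log-scale analysis (where all values are positive) or an exact sign-flip test of the paired differences is reported as a sensitivity analysis.

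The deadline is before outcome data are examined, not before unblinding, because treatments are coded (B5.3) and contrasts between coded arms could be seen while staff are still blinded.

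The cost is one paragraph and slightly more analysis work; the sample size and sampling schedule do not change. With normal differences the sign-flip test has power 0.770-0.786, against 0.792-0.810 for the t test. A loss of about 2-3 points matters little in a sensitivity analysis.

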Rapid deployment to remote mountainous regions will occur during MDO. Unacclimatized Service members experience altered carbohydrate metabolism, causing an increased reliance on glycogen for fuel, concomitant with a blunted ability to take up and oxidize exogenous carbohydrate. These negative physiological effects likely exacerbate declines in physical performance at HA. This proposal directly supports the Military Operational Medicine Research Program's Physiological Health and Performance Program Area under the Biomedical Performance Enhancement (BPE) Work Unit. Specifically, the proposed work aligns to BPE Strategic Plan's *Technical Objective 1.1.3: Material solutions (pharmacological) that enhance Soldier resistance to environmental stressors*.

This proposal will provide guidance for use of PIO to enhance exogenous carbohydrate oxidation at HA operations, and will provide the opportunity to determine if carbohydrate supplementation can indeed enhance performance if substrate metabolic dysregulation is avoided during HA exposure. Information from this proposal would be valuable to operational partners such as USSOCOM and the 10th Mountain Division who engage in HA MDO.

B4. OBJECTIVES/SPECIFIC AIMS/RESEARCH QUESTIONS

Objective:

1. Determine the effects of PIO on exogenous glucose oxidation and glucose turnover during exercise under acute HA exposure compared to PLA.
2. Determine the effects of PIO on inflammation during acute HA exposure compared to PLA.
3. Determine the effects of PIO on markers of iron status during acute HA exposure compared to PLA.

Hypotheses:

1. Exogenous glucose oxidation, Rd, and MCR during metabolically-matched, steady-state exercise at HA will be greater after PIO administration compared to PLA.
2. Inflammation will be lower during acute HA exposure after PIO administration compared to PLA.
3. Markers of iron status will be altered during acute HA exposure after PIO administration compared to PLA.

B5. RESEARCH PLAN

B5.1 Research Design

This study will be a randomized crossover double blind placebo control trial.

Table 1: Study Timeline

Study Day	Baseline					Trial 1					Washout	Trial 2				
	SV	1	2	3	4	5	6	7	8	9		20	21	22	23	24
Medical Screening	X															
Body Composition		X														
Height		X														
Weight		X								X						X
VO ₂ peak		X	X													
High Altitude Exposure			X							X						X
Practice Exercise				X	X											
Glycogen Normalization						X							X			

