PIO/PLA						X	X	X	X	X		X	X	X	X	X
Study Diet						X	X	X	X			X	X	X	X	
Steady-State Exercise										X						X
Carbohydrate Tracer Study										X						X
Blood Sampling										X						X
Breath Sampling										X						X

Timeline may shift based on participant availability, weekend, and holiday schedules.

B5.2 Research Subjects/Population(s)

B5.2.1 Subject Population(s)

Subject population will be representative of active duty male service members, being in good health and recreationally active. Previous studies at USARIEM (Protocol# 16-02HC and 18-09H) which have evaluated metabolically-matched exercise at HA compared to SL have only been performed in male volunteers. It is apparent that sex-based differences exist during low-to-moderate intensity endurance exercise at sea level. Sex-based differences in substrate oxidation during exercise at SL may result in differences in response to change in substrate oxidation at HA between men and women. Therefore, this study will recruit male volunteers only as sex differences in glucose metabolism at HA are not known. Based on findings from this and our previous studies, a similar series of investigations will be conducted in the future to assess the impact that unacclimatized HA exposure on females.

B5.2.2 Number of Subjects, Records, and/or Specimens

To complete testing on the 8 volunteers necessary to reach statistical power, we estimate we will need to enroll 24 individuals. All screening will stop once complete data has been collected on 8 volunteers. Records and specimen collection are described in the Research Procedures and Data Collection sections. During briefings and consenting potential participants will be informed that even though they may be eligible and want to participate, if we are able to obtain enough data from preceding subjects, they may not ultimately be tested. These individuals may be recruited from the HRV population, civilians, and active duty military personnel (on and off the installation).

B5.2.3 Inclusion Criteria

- Men aged 18 – 39 years
- Born at altitudes less than 2,100 m
- Physically active (exercise minimum 2 days per week)
- Have supervisor approval (permanent party military and civilians)
- Willing to refrain from alcohol, smokeless nicotine products and dietary supplement use during study periods

B5.2.4 Exclusion Criteria

- Born at altitudes greater than 2,100 m
- Musculoskeletal injuries that compromise exercise capability

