This randomized crossover placebo controlled double blinded study will examine substrate oxidation and glucose kinetic responses to ingesting supplemental carbohydrate (glucose) during metabolically-matched, steady-state exercise with acute (~5 h) exposure to HA (460 mmHg) after short-term (5 days) use of Pioglitazone (HA+PIO), or matched placebo (HA+PLA). Eight healthy, recreationally active males between the ages of 18-39 yrs will be enrolled. Following a muscle glycogen normalization period, volunteers will complete 80-min of metabolically-matched, steady-state (same absolute workload corresponding to $\sim 55 \pm 5\%$ of $\dot{V}O_{2\text{peak}}$ at HA) exercise on a treadmill, and consume 145 g of glucose (1.8 g/min) with HA+PIO and HA+PLA. A dual glucose tracer (^{13}C -glucose oral ingestion and $[6,6-^2\text{H}_2]$ -glucose primed, continuous infusion) technique and indirect calorimetry will be used to analyze endogenous and exogenous glucose oxidation, as well as glucose rate of appearance (Ra), disappearance (Rd), and MCR. Serial blood samples will be collected during each trial to assess endocrine and circulating substrate responses to exercise, carbohydrate, and hypoxia, with or without PIO. Isotope methodology and aerobic exercise protocols will be identical to our previous work (3, 4), allowing comparison of outcomes across studies. All

trials will be conducted in the USARIEM hypobaric/hypoxic chamber and be separated by a minimum 10-d washout period.

A member of the research team will generate a randomization scheme using a random number generator (<http://randomization.com> or similar). Treatment type (PIO/PLA) will be coded to de-identify treatment (Example: treatment A and treatment B or similar) to blinded staff. Assigned unblinded staff, responsible for administering the treatment to volunteers, will be responsible for creating treatment codes to match treatment. They will maintain record of randomization scheme and treatment.

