Volunteers who participate in the study will receive \$50.00 per blood sample (9 samples per CHO tracer trial day; 2 CHO tracer trial days per volunteer equals 18 samples for entire study), for a total of \$900.00 for completing the study. Volunteers will not be compensated for blood draws completed during the screening/medical clearance visit. Should volunteers withdraw, they will be compensated for any blood samples they complete except for the initial blood sample during the medical screening. Payments will be processed when the volunteer concludes the study (end of study period or voluntary withdrawal), as a total lump-sum payment, received as a direct deposit.

Note: Participants who receive more than \$600 in a calendar year will have this income reported to the Internal Revenue Service.

C3. WITHDRAWAL FROM RESEARCH PARTICIPATION

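### The two-period crossover is analysed without a period term, and no rule balances treatment order among the 8 completers

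*Combined protocol and SAP*

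**What the plan says.** B5.1 sets the design: "This study will be a randomized crossover double blind placebo control trial". Each volunteer has two experimental days, shown in Table 1 as days 9 and 24.

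B5.8.2 plans two kinds of analysis. For gas exchange, total substrate oxidation, and plasma, muscle and liver glucose oxidation: "Paired T tests will be used to assess effects of study arms (HA+PIO vs. HA+PLA"). For breath enrichment, exogenous glucose oxidation and blood analytes: "Mixed Model repeated measures ANOVA will be used to assess the effects of condition, time, and their interactions". Table 3 shows that time means minutes within a trial day. No period, order or sequence term appears in the document.

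On allocation, B5.3 says: "A member of the research team will generate a randomization scheme using a random number generator". It states no ratio, block size or replacement rule. B5.2.2 ends accrual by a count of completers: "All screening will stop once complete data has been collected on 8 volunteers". B5.8.1 adds: "We will request to enroll up to 24 individuals to account for withdrawals from the study".

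**The concern.** A paired difference between pioglitazone and placebo is also a difference between trial 2 and trial 1, with a sign set by the volunteer's sequence. If trial 2 is systematically different, that shift is added to the difference in one sequence and subtracted in the other. An analysis that ignores period either treats it as noise (equal sequences) or lets part of it into the treatment estimate (unequal sequences).

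The documents describe periods that are not identical. Trial 1 takes half of the blood: B5.3 has "taking ~340 mL of blood sampled from each volunteer over the experimental trial days", and C2 gives "9 samples per CHO tracer trial day; 2 CHO tracer trial days per volunteer equals 18 samples for entire study", so about 170 mL is drawn at trial 1 if volumes are equal, 15 days before trial 2 (24 − 9). Hemoglobin, ferritin, erythropoietin and other iron markers are outcomes under objective 3. Volunteers also reach trial 2 with one more altitude exposure of about 7 hours and one more 80-minute bout.

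An order effect is therefore plausible, but nothing in the documents gives its size. At stake are the paired t tests and the condition main effect in the mixed model, in a trial with only 8 completers.

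**Working it through.** **The plan's own figure.** B5.8.1 states 8 for 80% power; Table 4 lists effect sizes 1.11, 0.95 and 0.98 with n of 7, 8 and 7. Alpha and sidedness are not stated. Taking the effect sizes as standardised paired differences and alpha as 5%, the noncentral t gives n = 7, 9, 8 one-sided and 9, 11, 11 two-sided. Power at n = 8 is 88.0%, 78.0%, 80.1% one-sided and 76.8%, 63.7%, 66.4% two-sided. So 8 is reproduced approximately one-sided. A two-sided paired t test has 80% power at n = 8 for an effect of about 1.16. The calculations below use 1.16 (assumed) and 0.95 (Table 4), two-sided unless stated.

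**Model.** Let d be the treatment effect and P the trial-2-minus-trial-1 shift, both in SDs of the paired difference. P is assumed to lie between 0 and 1. Volunteers taking placebo first have difference d + P + e; those taking pioglitazone first have d − P + e; SD(e) = 1. With n₁ and n₂ completers in the two sequences (n₁ + n₂ = 8):

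- Unadjusted mean difference: expectation d + P(n₁ − n₂)/8. Its error sum of squares is noncentral chi-square on 7 df with noncentrality 4n₁n₂P²/8, which is 8P² at 4:4.
- Period-adjusted estimate (average of the two sequence means): unbiased for d at any split with both sequences present, SE √[(1/n₁ + 1/n₂)/4], 6 df.

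**Power at 4:4.** The expected error variance of the paired t test is 1 + 8P²/7, which is 1.29 at P = 0.5 and 2.14 at P = 1.

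| d | P = 0 | 0.25 | 0.5 | 1 | Period-adjusted, any P |
|---|---|---|---|---|---|
| 1.16 | 80.3% | 78.1% | 71.7% | 47.3% | 78.0% |
| 0.95 | 63.7% | 61.0% | 53.4% | 29.6% | 61.3% |
| 0.95, one-sided | 78.0% | 76.0% | 70.3% | 49.5% | 76.6% |

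Two-sided, the methods break even at P = 0.26 (d = 1.16) and P = 0.23 (d = 0.95). Below that the plain paired t test is slightly better.

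**Estimate at uneven splits.** Bias is P(5 − 3)/8 = 0.25P at 5:3 and P(6 − 2)/8 = 0.5P at 6:2. With P = 0.5 at 6:2, a true effect of 0.95 is estimated on average as 0.95 + 0.25 = 1.20 or 0.95 − 0.25 = 0.70, depending on which sequence is larger.

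**Type I error of the paired t test.** At P = 0.5 it is 3.0% (4:4), 3.9% (5:3) and 6.8% (6:2); at P = 1 it is 0.7%, 2.0% and 8.5%. Weighted over simple randomisation of 8, it is 5.0% at P = 0.5 and 5.3% at P = 1.

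**How often the split is uneven.** With unblocked allocation, Binomial(8, 0.5) gives 4:4 in 70/256 = 27%, 5:3 in 112/256 = 44%, and 6:2 or worse in 74/256 = 29%. Blocks of 4 with no replacement rule, taking the first 8 completers of up to 24, give 4:4 in 71%, 51% and 38% of simulated trials at assumed post-randomisation losses of 10%, 25% and 50%.

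**Where it does not apply.** If the shift is constant across the day, it cancels from the condition-by-time interaction. Simulated type I error there was 4.9–5.0% at 4:4 and 6:2 for P from 0 to 1 (two time points, assumed correlation 0.5).

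**The case against.** The harm depends on a quantity that the documents do not supply, and the design already works against it: a baseline altitude exposure, practice sessions, fixed speed and grade, the same diet and repeated glycogen normalization, and a washout of at least 10 days. Below a shift of about 0.25 SD the planned test is the better one. Averaged over randomisation, bias is zero and type I error close to 5%. All of this stands, so the point is one of efficiency and conditional bias, not of an invalid test.

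Effect size matters too. Table 4's delta divided by its SD gives 0.35/0.21 = 1.67, 0.09/0.06 = 1.50 and 3.1/2.0 = 1.55. If those are SDs of paired differences, which is not stated, then at d = 1.5 and 4:4 power is 95% with no shift and 91% unadjusted against 94% adjusted at P = 0.5. The gain is then small unless P is near 1 (75% against 94%). The calculations also use one summary difference per volunteer, while exogenous glucose oxidation goes into a mixed model whose random-effects structure is not given. These points affect the size of the gain, not its direction once P exceeds the break-even.

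Finally, a period term on its own can lose power at uneven splits. That is correct, and it is why the two changes belong together.

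**Conclusion.** The concern holds. Neither planned analysis contains period, and no stated rule makes the 8 completers 4:4. If an order effect exists, it costs power at 4:4 and shifts the estimate by a quarter (5:3) or half (6:2) of its size. At a shift of 0.5 SD the loss relative to a period-adjusted analysis at 4:4 is about 6 points of two-sided power at d = 1.16 (72% against 78%) and 8 at d = 0.95 (53% against 61%). At 1 SD it exceeds 30 points in both cases.

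This rests on an assumed shift of 0 to 1 SD, a 5% two-sided test and one summary difference per volunteer. The change is worth making because it is cheap. Confidence in the size of the benefit is moderate, because the documents give no estimate of the order effect.

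**What to change.** Make both changes together.

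1. **B5.3 and B5.2.2.** Generate the two sequences 1:1 in permuted blocks. Have the unblinded staff who already hold the scheme assign each replacement to the sequence of the volunteer replaced, so that accrual ends with four completers per sequence.
2. **B5.8.2.** Add period as a fixed effect to the mixed model (volunteer random; condition, time, condition-by-time and period fixed). For the physiological outcomes now given paired t tests, use the period-adjusted within-volunteer contrast (volunteer random; treatment and period fixed). Chamber conditions can keep the paired t test. Report the period estimate. Rd and MCR, named in hypothesis 1, are assigned to neither analysis at present and should be placed in the same edit.

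The cost is wording, with no extra volunteers or procedures, and one error degree of freedom (7 to 6). With no order effect and d = 1.16, power goes from 80% to 78% at 4:4, but to 75% at 5:3 and 66% at 6:2. The period term should therefore not be added without the balancing rule, and the plan should say in advance what is done if the 24 places run out before 4:4 is reached.
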